6.3 ADVERSE EVENTS

All adverse events will be described in the source documents

6.3.1 The following adverse events of any grade will be captured in C3D:

- Abscess formation
- Fistula formation
- Length of Stay (LoS) >14 days (LoS is defined as the time in days from the date of the procedure until the date that discharge criteria are met).

NOTE: If the discharge criteria date is not the same as the actual date of discharge, the date the patient met discharge criteria should be documented in CRIS.

6.3.2 Exclusions to Routine Adverse Event Reporting

The following Adverse Events will be captured only in the source documents and will not be reported in C3D.

- For the duration of the study
 - Laboratory values that do not support the diagnosis of a reportable event with the exception of noted events in section 6.3.2.
 - All grade 1 events
- During hospitalization for surgical resection
 - Grade 1 and 2 events
 - Grade 3 and 4 events which resolve during the first 72 hours following surgery
- Post-operative recovery phase (following discharge)
 - Grade 1 and 2 events
 - Events that result in a hospitalization for convenience will not be reported.
- During the follow up period (more than 30 days following the last treatment)
 - Only those events that are serious, unexpected, and related to the treatment will be captured in C3D.

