1.1.2 Secondary Objectives

- Determine morbidity of this procedure in this patient population
- Determine the impact of surgery and HIPEC on QOL
- Determine the impact of surgery and HIPEC on hormone excess
- Examine patterns of recurrence (local versus systemic)
- Perform molecular analyses to try to discern if there are intrinsic differences between tumors that recur widely throughout the peritoneal surface and those that metastasize to other organs or are confined to a local recurrence.
- Determine overall survival after optimal debulking and heated intraperitoneal chemotherapy with cisplatin in patients with intraperitoneal spread of adrenocortical cancer.

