2.1.2 Exclusion Criteria

- Concomitant medical problems that would place the patient at unacceptable risk for a major surgical procedure.
- History of congestive heart failure and/or an LVEF < 40%
- **Note:** Patients at increased risk for coronary artery disease or cardiac dysfunction (e.g., >65yo, diabetes, history of hypertension, elevated LDL, first degree relative with coronary artery disease) will undergo full cardiac evaluation and will not be eligible if they demonstrate significant irreversible ischemia on stress thallium or an ejection fraction <40%.
- Significant COPD or other chronic pulmonary restrictive disease with PFT's indicating an FEV1 less than 50% or a DLCO less than 40% predicted for age
Note: Patients who have shortness of breath with minimal exertion or who are at risk for pulmonary disease (e.g., chronic smokers) will undergo pulmonary function testing and will not be eligible if their FEV1 is < 50% of expected.
- Grade 2 or greater neuropathy
- Women of child-bearing potential who are pregnant or breastfeeding because of the potentially dangerous effects of the chemotherapy on the fetus or infant.
- Brain metastases or a history of brain metastases
- Childs B or C cirrhosis
- Evidence of severe portal hypertension by history, endoscopy, or radiologic studies
Note: Any diagnosis of portal hypertension or clinical stigmata of such including but not limited to gastric or esophageal varices, umbilical vein varices or telangectasias.
- Weight < 30 kg

- Active systemic infections, coagulation disorders or other major medical illnesses of the cardiovascular, respiratory or immune system, myocardial infarction, cardiac arrhythmias, obstructive or restrictive pulmonary disease

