3.11 TREATMENT ASSESSMENT AND RESPONSE (FOLLOW UP PERIOD)

- Because of the nature of peritoneal imaging and because cytoreductive surgery will likely eliminate all imageable disease, response can only be measured in terms of radiographic disease-free survival. At any time point when there is evidence of progressive disease (imageable tumor nodules or increasing ascites persistent on CT scans as interpreted by the official interpretation of the imaging studies) the patients will be scored as progressive disease. In some cases this may require successive scans, but the time of

recurrence will be retrospectively defined at the point the first scan demonstrated imageable disease.

- Patients will be evaluated 3 months from the operative date (+/- 1 month) intervals for the first year; every four months for (+/- 1 month) the next year and then q 6 months (+/- 1 month) thereafter.
- The following evaluations will be performed at each visit:
 - Imaging studies
 - Physical examination to include ECOG, weight and vital signs
 - Tumor markers as indicated
 - CBC, acute care, mineral and hepatic panel, CRP, Albumin, pre-albumin, ferritin, Hgb A1c if elevated pre-op.
 - Completion of Health related Quality of Life Forms (HRQOL) – at the first follow up visit and then at each evaluation until off study.
- Patients who are unwilling or unable to return for follow up evaluation will be followed every 6 months by phone contact until off study criteria are met. The following information may be obtained:
 - Summary of treatment received since the previous contact
 - Estimation of ECOG status
 - Request for imaging studies, physical exam and laboratory reports to be sent to the PI

Note: if patient is taken off study prior to 1 year following surgery, the HRQOL will be completed at the off study evaluation if possible.

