10.1.5 Toxicities

Cisplatin produces renal tubular toxicities associated with renal insufficiency and electrolyte, (i.e. magnesium, potassium, calcium, phosphate, bicarbonate) wasting which may result in significant hypomagnesemia and hypokalemia. Neurotoxicity manifests as both sensory and motor peripheral neuropathies. Cisplatin is also toxic to the 8th cranial nerve producing ototoxicity which consists primarily of deficits in high frequency auditory acuity, but may include vestibular abnormalities. Systemic administration of cisplatin at doses similar to those planned in this study are associated with significant nausea and vomiting and bone marrow suppression, particularly leukopenia and thrombocytopenia. Transient moderate elevations of hepatic transaminases, (i.e. AST, ALT) and acute systemic allergic reactions including anaphylaxis may also occur. The prior Phase I study of CHPP with cisplatin has not identified any regional intraperitoneal toxicity from cisplatin. The dose limiting systemic toxicity was renal toxicity at doses of 350 mg/M². No other systemic toxicities were identified at that dose level.

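### Neuropathy and hearing loss are named as cisplatin toxicities but not prompted for after treatment, and section 6.3.2 keeps early low-grade and late non-serious cases out of C3D, so a low count could not be told apart from non-capture.

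*Combined protocol and SAP*

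**What the plan says.** - Section 1.1.2 sets the secondary objective: "Determine morbidity of this procedure in this patient population". Section 8 gives no analysis for it and names no data source.
- Section 10.1.5 lists the cisplatin toxicities, among them: "Neurotoxicity manifests as both sensory and motor peripheral neuropathies" and "Cisplatin is also toxic to the 8th cranial nerve producing ototoxicity which consists primarily of deficits in high frequency auditory acuity".
- Section 2.1.2 excludes patients with "Grade 2 or greater neuropathy", so a neuropathy grade is implied once, at eligibility. The screening list in 2.2 has a history and physical examination but no hearing item.
- The recovery visit (3.10) and each follow-up visit (3.11) list the same examination: "Physical examination to include ECOG, weight and vital signs". Laboratory panels, tumor markers, imaging and a quality-of-life form are added. Section 3.13 asks for a safety visit at about 30 days and does not state its content.
- Section 6.3.1 captures three items in C3D at any grade: abscess, fistula and a stay longer than 14 days.
- Section 6.3.2 leaves grade 1 events out of C3D throughout, and grade 1 and 2 events in hospital and in recovery after discharge. More than 30 days after treatment the rule is: "Only those events that are serious, unexpected, and related to the treatment will be captured in C3D".
- Section 7.1.1 requires adverse events on the case report form except where 6.3.2 says otherwise, so 6.3.2 controls.

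**The concern.** Most of the other toxicities in 10.1.5 (renal, electrolyte, marrow and hepatic) would show up in the scheduled blood tests. Neuropathy and hearing loss would not. They are found only if the patient mentions them or someone asks, and no post-treatment visit asks. The quality-of-life form, as Appendix C describes it, covers general well-being and colon or abdominal symptoms, with no neuropathy or hearing scale.

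The capture rules then act on what is found. A patient who enters with grade 0 or 1 neuropathy and worsens to grade 2 during recovery has reached the level that would have barred entry, yet does not enter C3D. Hearing has a further problem. Section 2.1.1 admits patients with residual toxicity up to grade 2 from prior chemotherapy, so without a baseline a later deficit could not be separated from an old one.

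What is at stake is the morbidity objective: absence of capture could be reported as absence of harm.

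**Working it through.** The plan gives no morbidity figure to reproduce. Its one design figure, 80% power with 24 patients, does not bear on this point.

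**Step 1. The rules by period, for a neuropathy or hearing event.**

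| Event | Enters C3D under 6.3.2? | Held elsewhere |
|---|---|---|
| Grade 1, any time | No | Source documents (6.3) |
| Grade 2, in hospital or recovery | No | Source documents; IRB table if unexpected and related, or if serious (7.2.2) |
| Grade 3–4 in hospital, resolved within 72 hours | No | Source documents; IRB table if related |
| Grade 3–4, not resolved within 72 hours, up to day 30 | Yes | IRB table if related |
| Non-serious, any grade, first arising after day 30 | No | Source documents; IRB table if grade 3–4 and related |
| Serious, related but expected, after day 30 | No | Recorded and reported under 7.1.1; IRB table |
| Serious, unexpected and related, grade 2 or higher, after day 30 | Yes | Recorded and reported under 7.1.1; IRB table |

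Two conflicts follow. Section 7.1.1 has late, at least possibly related serious events recorded with no requirement that they be unexpected; 6.3.2 adds that requirement. Section 7.2.2 wants all related grade 3–4 events tabulated, but after day 30 C3D cannot supply the non-serious ones.

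**Step 2. Timing.** The first clinic visit is at about 4–8 weeks, that is 4 × 7 = 28 to 8 × 7 = 56 days. Of that 28-day span, only the first 2 days (28 to 30) precede the day-30 cut. An event first noticed at that visit will usually be dated in the strictest window, unless the unspecified 30-day safety visit finds it.

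**Step 3. Size, under assumptions.** Let N = 24 evaluable patients (section 3.1), q = true any-grade incidence, g = share at grade 3 or higher, and s = share of those falling in a recorded window. The documents give none of q, g or s.

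Expected patients in C3D = N × q × g × s, and P(zero in C3D) = (1 − q × g × s)^N.

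- Low end: 24 × 0.10 × 0.05 × 0.25 = 0.03, P(zero) = 97%; affected 24 × 0.10 = 2.4.
- Middle: 24 × 0.30 × 0.10 × 0.50 = 0.36, P(zero) = 0.985^24 = 70%; affected 24 × 0.30 = 7.2.
- High end: 24 × 0.50 × 0.40 × 1 = 4.8, P(zero) = 0.80^24, below 1%; affected 24 × 0.50 = 12.

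The formula assumes that every case is elicited, which is generous without a prompt. It ignores the rare late grade 2 event that is serious, unexpected and related.

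**Step 4. What a zero would be taken to mean.** With 0 of 24, the one-sided 95% upper bound is 1 − 0.05^(1/24) = 11.7%. That bound applies to captured events. In the middle case the true any-grade rate is 30% and a zero is still the likelier result.

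**The case against.** The strongest reply is that nothing is thrown away. Section 6.3 puts all adverse events in the source documents, and 7.1.1 counts patient-reported events and has every event followed to baseline or stabilization. Grade 3–4 events not resolved within 72 hours reach C3D up to day 30, and 7.2.2 tabulates related grade 3–4 events and all serious events for the IRB. Section 10.1.5 states no severity for either toxicity, so under 7.1.3 a severe case might count as unexpected. No section says that morbidity will be analyzed from C3D alone.

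The reply also has evidence. Of the Phase I trial, where renal toxicity was dose-limiting at 350 mg/m², section 10.1.5 says: "No other systemic toxicities were identified at that dose level". The dose stated here is 250 mg/m² with thiosulfate to limit systemic toxicity, so a low rate may be real.

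Much of this stands. It rules out an inference that a reader might draw, that the morbidity result will show almost none of these events by construction. The documents give no incidence, some severe events are captured, and the assumed range in Step 3 is too wide to support it.

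Three things are left unanswered. Source documents hold only what is elicited or volunteered. An event after day 30 must still be serious, whatever its expectedness. And if the true rate is low, this plan could not show it.

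**Conclusion.** The point holds as one about capture. After treatment neither toxicity is prompted for, and hearing has no stated baseline. Grade 1–2 events in hospital and recovery cannot enter C3D, nor can non-serious events of any grade first arising more than 30 days after treatment. A zero or low C3D count would therefore be uninterpretable for these two toxicities.

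The size of any under-count is unknown. The middle case (7.2 affected, 0.36 expected in C3D, 70% chance of zero) rests wholly on assumed rates. The conclusion also assumes that the morbidity summary will draw on C3D, which 7.1.1 suggests but section 8 does not state.

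A reader might also infer that neuropathy is never graded or that all late events are lost. Neither is right: eligibility implies one neuropathy grade, and 7.1.1 and 7.2.2 retain some late events. The primary endpoint and sample size are unaffected. The change is worth making because it is cheap and the gap cannot be reliably repaired afterwards.

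**What to change.** 1. Add to the any-grade list in 6.3.1, exempt from 6.3.2: peripheral neuropathy and hearing loss or tinnitus, worse than baseline, at any time on study.
2. Record a symptom-based grade for each, on a named scale (sections 6.3 and 7 name none), at baseline, at the recovery visit in 3.10 and at each follow-up visit in 3.11.
3. Reconcile 6.3.2 with 7.1.1 and 7.2.2 on events after day 30, so that late serious events fall under one rule and C3D can supply the IRB table.

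The cost is two form lines per visit, with no new visit, procedure or change in sample size. The limitation is that 10.1.5 describes the hearing deficit as mainly high-frequency, which symptom-based grading without audiometry may miss; the report should say so.

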7 SAFETY REPORTING REQUIREMENTS/DATA AND SAFETY MONITORING PLAN

7.1 DEFINITIONS

7.1.1 Adverse Event

An adverse event is defined as any reaction, side effect, or untoward event that occurs during the course of the clinical trial associated with the use of a drug in humans, whether or not the event is considered related to the treatment or clinically significant. For this study, AEs will include events reported by the patient, as well as clinically significant abnormal findings on physical

examination or laboratory evaluation. A new illness, symptom, sign or clinically significant laboratory abnormality or worsening of a pre-existing condition or abnormality is considered an AE. All AEs must be recorded on the AE case report form unless otherwise noted above in Section 6.3.2.

All AEs, including clinically significant abnormal findings on laboratory evaluations, regardless of severity, will be followed until return to baseline or stabilization of event. Serious adverse events that occur more than 30 days after the last administration of investigational agent/intervention and have an attribution of at least possibly related to the agent/intervention should be recorded and reported as per section 7.2.

7.1.2 Suspected adverse reaction

Suspected adverse reaction means any adverse event for which there is a reasonable possibility that the drug caused the adverse event. For the purposes of safety reporting, 'reasonable possibility' means there is evidence to suggest a causal relationship between the drug and the adverse event. A suspected adverse reaction implies a lesser degree of certainty about causality than adverse reaction, which means any adverse event caused by a drug.

7.1.3 Unexpected adverse reaction

An adverse event or suspected adverse reaction is considered "unexpected" if it is not listed in the investigator brochure or is not listed at the specificity or severity that has been observed; or, if an investigator brochure is not required or available, is not consistent with the risk information described in the general investigational plan or elsewhere in the current application.

"Unexpected", also refers to adverse events or suspected adverse reactions that are mentioned in the investigator brochure as occurring with a class of drugs or as anticipated from the pharmacological properties of the drug, but are not specifically mentioned as occurring with the particular drug under investigation.

7.1.4 Serious

An Unanticipated Problem or Protocol Deviation is serious if it meets the definition of a Serious Adverse Event or if it compromises the safety, welfare or rights of subjects or others.

7.1.5 Serious Adverse Event

An adverse event or suspected adverse reaction is considered serious if in the view of the investigator or the sponsor, it results in any of the following:

- Death,
- A life-threatening adverse drug experience
- Inpatient hospitalization or prolongation of existing hospitalization
- Persistent or significant incapacity or substantial disruption of the ability to conduct normal life functions
- A congenital anomaly/birth defect.
- Important medical events that may not result in death, be life-threatening, or require hospitalization may be considered a serious adverse drug experience when, based upon appropriate medical judgment, they may jeopardize the patient or subject and may require medical or surgical intervention to prevent one of the outcomes listed in this definition.

Note: Events that result in a hospitalization for convenience will not be reported.

7.1.6 Disability

A substantial disruption of a person's ability to conduct normal life functions.

7.1.7 Life-threatening adverse drug experience

Any adverse event or suspected adverse reaction that places the patient or subject, in the view of the investigator or sponsor, at immediate risk of death from the reaction as it occurred, i.e., it does not include a reaction that had it occurred in a more severe form, might have caused death.

7.1.8 Protocol Deviation (NIH Definition)

Any change, divergence, or departure from the IRB approved research protocol.

7.1.9 Non-compliance (NIH Definition)

The failure to comply with applicable NIH Human Research Protections Program (HRPP) policies, IRB requirements, or regulatory requirements for the protection of human research subjects.

7.1.10 Unanticipated Problem

Any incident, experience, or outcome that:

- Is unexpected in terms of nature, severity, or frequency in relation to
 - (a) the research risks that are described in the IRB-approved research protocol and informed consent document; Investigator's Brochure or other study documents, and
 - (b) the characteristics of the subject population being studied; AND
- Is related or possibly related to participation in the research; AND
- Suggests that the research places subjects or others at a greater risk of harm (including physical, psychological, economic, or social harm) than was previously known or recognized.

7.2 NCI-IRB AND CLINICAL DIRECTOR REPORTING

7.2.1 NCI-IRB and NCI CD Expedited Reporting of Unanticipated Problems and Deaths

The Protocol PI will report in the NIH Problem Form to the NCI-IRB and NCI Clinical Director:

- All deaths, except deaths due to progressive disease
- All Protocol Deviations
- All Unanticipated Problems
- All non-compliance

Reports must be received within 7 days of PI awareness via iRIS.

7.2.2 NCI-IRB Requirements for PI Reporting at Continuing Review

The protocol PI will report to the NCI-IRB:

1. A summary of all protocol deviations in a tabular format to include the date the deviation occurred, a brief description of the deviation and any corrective action.
2. A summary of any instances of non-compliance

3. A tabular summary of the following adverse events:
 - All Grade 2 unexpected events that are possibly, probably or definitely related to the research;
 - All Grade 3 and 4 events that are possibly, probably or definitely related to the research;
 - All Grade 5 events regardless of attribution;
 - All Serious Events regardless of attribution.

NOTE: Grade 1 events are not required to be reported

7.3 DATA AND SAFETY MONITORING PLAN

7.3.1 Principal Investigator/Research Team

The clinical research team will meet on a weekly basis when patients are being actively treated on the trial to discuss each patient.

All data will be collected in a timely manner and reviewed by the principal investigator or a lead associate investigator. Adverse events will be reported as required above. Any safety concerns, new information that might affect either the ethical and or scientific conduct of the trial, or protocol deviations will be immediately reported to the IRB using iRIS.

The principal investigator will review adverse event and response data on each patient to ensure safety and data accuracy. The principal investigator will personally conduct or supervise the investigation and provide appropriate delegation of responsibilities to other members of the research staff.

8 STATISTICAL CONSIDERATIONS

The primary objective of this trial is to conduct a pilot study to determine if the use of debulking surgery and HIPEC in patients with intra-peritoneal spread of adrenocortical carcinoma is able to be associated with an intra-peritoneal progression free interval which may exceed that of the use of chemotherapy alone.

Data from a recently published study indicated that a 5.0 month median PFS¹⁴ may be attained in similar patients using EDP and mitotane. This will be a single arm trial with the goal of seeing if the proposed combination of HIPEC and surgery may be associated with a 10 month median PFS. Using the method of Brookmeyer and Crowley³³, the study will plan to enroll 24 fully evaluable patients over a 60 month period. Based on this method, with 24 subjects, there would be 80% power to determine if there is a median PFS of 10 months rather than 5 months, based on a one-tailed 0.10 alpha level test. In practice, Kaplan-Meier curves and appropriate confidence intervals at selected time points will be provided to help interpret the results relative to historical results.

At the rate of 6 patients per year, 24 evaluable patients could be enrolled in 5 years, allowing for a ceiling of 30 patients to account for patients who may be inevaluable.

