- Cisplatin is one of the most effective chemotherapeutic agents for ACC. In the Surgery Branch we have conducted Phase I and II trials using heated intraperitoneal (IP) chemotherapy with cisplatin for primary peritoneal mesothelioma, low grade appendiceal adenocarcinoma, ovarian malignancies, and high grade adenocarcinoma of the gastrointestinal tract. Synergy has been demonstrated for cisplatin and hyperthermia
- The purpose of this trial is to determine if an aggressive surgical approach with intraperitoneal administration of heated cisplatin when tumor volume is minimal, can impact and improve on progression free survival.

Objective:

- To determine IP progression free survival after optimal debulking and heated IP chemotherapy with cisplatin in patients with IP spread of adrenocortical cancer

Eligibility:

- Histologically proven ACC evaluable by CT imaging with the majority of disease confined to the peritoneal cavity and surgically resectable to a residual size of less than 1 cm or amenable to radiofrequency ablation in patients who are > 18 years of age.

Design:

- This is a classic phase 2 trial to determine efficacy of this therapeutic strategy in ACC. Patients will undergo cytoreductive surgery to achieve a CCR of 0 or 1. Patients who are successfully debulked will then undergo HIPEC with cisplatin. Patients will be evaluated by associate investigators in coordination with the Principal Investigator for eligibility. Due to its exploratory nature, up to 30 patients may be enrolled to obtain 24 evaluable patients. (Patients must undergo successful debulking and HIPEC to be considered evaluable.)

TABLE OF CONTENTS

PRECIS	3
TABLE OF CONTENTS.....	4
1 INTRODUCTION.....	6
1.1 Study objectives	6
1.2 Background and Rationale	6
2 ELIGIBILITY ASSESSMENT AND ENROLLMENT	9
2.1 Eligibility Criteria	9
2.2 Screening Evaluation.....	11
2.3 Registration Procedures.....	12
2.4 Stratification Procedures	12
3 STUDY IMPLEMENTATION	12
3.1 Study Design	12
3.2 Preoperative Patient Management.....	12
3.3 Patient Management in the Operating Room	13
3.4 Peritoneal metastasectomy and cytoreductive surgery.....	13
3.5 Intraperitoneal Chemotherapy HIPEC	13
3.6 Medications	14
3.7 Post-Operative Care	14
3.8 Research Evaluations	15
3.9 Discharge.....	15
3.10 Post Discharge.....	15
3.11 Treatment Assessment and Response (Follow up period)	15
3.12 Measurement of Health Related Quality of Life	16
3.13 Criteria for Removal from Protocol Therapy and Off Study Criteria	17

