1 INTRODUCTION

1.1 STUDY OBJECTIVES

1.1.1 Primary Objective

- To determine intraperitoneal progression free survival after optimal debulking and heated intraperitoneal chemotherapy with cisplatin in patients with intraperitoneal spread of adrenocortical cancer

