1.2 BACKGROUND AND RATIONALE

1.2.1 Adrenocortical Carcinoma

Adrenocortical carcinoma (ACC) is a rare tumor with an incidence of 1.5 to 2 per million people per year¹⁻³. It has a very poor prognosis with an overall 5-year mortality rate of 75 - 90% and an average survival from the time of diagnosis of 14.5 months. Signs and symptoms due to excess hormonal secretion are seen in a large fraction of patients, further contributing to the morbidity associated with this disease.

The treatment of choice for a localized primary or recurrent tumor is surgical resection. Excisable primary tumors represent about 40% of cases at presentation; however, 60 - 80% of these patients eventually die from recurrent extensive metastases⁴. Patients with recurrent or metastatic disease are infrequently curable by surgery alone due to the propensity for intraperitoneal recurrence.

For unresectable metastatic or recurrent disease, mitotane, aminoglutethimide, metapyrone, and ketoconazole are used. Of these, mitotane is the only agent with both anti-tumor and adrenolytic effects. Aminoglutethimide, metapyrone, and ketoconazole are used to treat the symptoms of excess hormone production in patients with functional tumors. Mitotane, the most extensively studied agent, was reported to have response rates of 30-60% in older studies without standardized response criteria or the use of modern imaging technology⁵⁻⁷. Response rates of 20% or less have been noted with more modern imaging technology. These responses persist for an average of 10.5 months with no apparent impact on overall survival.

Most reports of cytotoxic therapy for ACC are anecdotal or include a small number of patients⁸⁻¹³. These studies report low response rates with the majority of responses classified as partial and

of less than one year in duration. Trials using mitotane in combination with various chemotherapeutic agents have had similar results^{12, 13}. The largest randomized trial for metastatic or locally advanced ACC conducted was recently published and showed that a regimen of etoposide, doxorubicin and cisplatin (EDP) combined with mitotane was superior to the combination of streptozocin and mitotane with a median PFS of 5.0 months vs. 2.1 months and response rate of 23.2 and 9.2% respectively¹⁴.

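### The primary endpoint is intraperitoneal PFS with undefined events, but section 8 takes its benchmark, target and power from plain PFS; the mismatch by itself tilts the comparison toward the strategy

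*Combined protocol and SAP*

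**What the plan says.** The endpoint carries three labels in the combined protocol and SAP.

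- **Intraperitoneal PFS.** Section 1.1.1: "To determine intraperitoneal progression free survival after optimal debulking". Section 8 opens the same way, asking whether the strategy is "associated with an intra-peritoneal progression free interval which may exceed that of the use of chemotherapy alone".
- **Plain PFS.** The precis and section 1.2.5 ask whether the approach "can impact and improve on progression free survival". In section 8 the null value is plain PFS ("Data from a recently published study indicated that a 5.0 month median PFS"), and so is the power statement: "there would be 80% power to determine if there is a median PFS of 10 months rather than 5 months", at a one-sided 0.10 level with 24 evaluable patients.
- **Radiographic disease-free survival.** Section 3.11: "response can only be measured in terms of radiographic disease-free survival".

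Section 1.2.1 gives the source of the 5.0 months: "The largest randomized trial for metastatic or locally advanced ACC", a comparison of systemic regimens.

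Section 3.11 is the only scoring rule. It begins from the difficulty of peritoneal imaging, but its criterion, "imageable tumor nodules or increasing ascites persistent on CT scans", is limited to no anatomical site and does not score death.

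Section 8 calls the study a pilot and sets no go/no-go rule. It promises Kaplan-Meier curves with confidence intervals, to be read against historical results.

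**The concern.** The quantity to be estimated and the quantity it is compared with are not the same. IP-PFS, if it counts only IP events, leaves out events that ordinary PFS includes. The benchmark is labelled PFS with no regional qualifier. That it counts any site and death is an inference from ordinary usage, because the source trial is not in the documents.

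No section says whether extraperitoneal progression or death is an event, a censoring or a competing event for IP-PFS, or whether a liver recurrence is IP. The plan foresees these cases:

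- resectable lung and liver metastases may enter (2.1.1);
- visceral metastatic disease is one of two strata (2.4);
- liver metastases without peritoneal disease may be treated (3.4);
- local versus systemic recurrence is a secondary objective (1.1.2);
- perioperative death is a listed risk (9.4).

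Under 3.13.2, progression that needs systemic therapy takes the patient off study. A treated lung relapse could therefore become a censored time in the primary curve.

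The 5.0-month figure is the only benchmark and the only powered comparison. Two analysts following the plan could draw different primary curves from the same data and disagree on whether chemotherapy alone had been exceeded.

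**Working it through.** **Inputs from section 8.** n = 24; null median 5 months; target 10 months; one-sided alpha 0.10; Brookmeyer-Crowley method.

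**Assumptions of this review.** Exponential times; no censoring before 5 months. f is the share of first progressions that are extraperitoneal and q the share of first events that are deaths. Neither is in the documents.

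**1. The plan's power.** Treat the method as a test of S(5) = 0.5. At a 10-month median, S(5) = 2^(-5/10) = 0.7071.

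- Null standard error: sqrt(0.25/24) = 0.1021, times 1.2816 = 0.1308.
- Alternative standard error: sqrt(0.7071 × 0.2929/24) = 0.0929.
- Power = Φ((0.2071 − 0.1308)/0.0929) = 79.4%.

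The stated 80% therefore reproduces when all events count.

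**2. A whole-number rule for illustration.** The normal cut-off is 12 + 1.2816 × 0.5 × sqrt(24) = 15.14, so success means at least 16 of 24 event-free at 5 months. This rule is the review's, not the plan's. Its exact error at S(5) = 0.5 is 0.076 and its exact power at 0.7071 is 0.751.

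**3. Direction.** Any patient with an IP event by time t has had some event by time t. IP-PFS is therefore at least as long as any-site PFS in the same patients.

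**4. Size when the true any-site median is 5 months (no gain).** Let h be the fraction of the all-event hazard that is counted. Then S(5) = 2^(-h), the apparent median is 5/h, and the chance of success is P(X ≥ 16) for X ~ Binomial(24, S(5)). Uncounted events are assumed to leave the later IP hazard unchanged.

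| Counting rule | h | f = 0.10 | f = 0.20 | f = 0.33 |
|---|---|---|---|---|
| Extraperitoneal progression ignored, no deaths (q = 0) | 1 − f | 0.14 | 0.24 | 0.44 |
| Same, q = 0.2, deaths count as events | 1 − 0.8f | 0.12 | 0.20 | 0.33 |
| Same, q = 0.2, deaths not counted | 0.8(1 − f) | 0.35 | 0.49 | 0.69 |

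First row in full: h = 0.90, 0.80, 0.67; S(5) = 0.536, 0.574, 0.629; apparent median 5.6, 6.3, 7.5 months.

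**5. Section 3.11 read as any site, deaths not counted.** With q = 0.2, h = 0.8, S(5) = 0.574 and the chance of success is 0.24. With q = 0, or with deaths counted, it returns to 0.076.

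**The case against.** **The tilt depends on a reading the text does not establish.** Section 3.11 restricts progression to no site, so read literally a nodule anywhere counts. This stands in part: on that reading extraperitoneal progression causes no tilt. The measured endpoint is then not the stated one. A reader might also infer that this reading leaves the design figures untouched. It does not, because 3.11 does not score death (step 5).

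**This is a pilot, with no decision rule and an unknown share.** That stands, and it is why the probabilities are illustrations. It does not remove the mismatch, since the curves are to be read against one historical figure.

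**The bias need not favour the strategy overall.** A reader might infer that any comparison with 5.0 months can only flatter the strategy. The documents do not support that. The ordering holds within the same patients. Against an external trial the net direction also depends on who was enrolled and how progression was scored. After cytoreduction any imageable nodule counts, and 3.11 dates recurrence back to the first scan that showed it.

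**There is no threshold share.** A reader might look for the extraperitoneal share at which the 0.10 level is passed. Any such value would be an artefact of the 16-of-24 rule, which starts at 0.076. A test sized exactly at 0.10 is exceeded by any positive share.

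**Regional control is a legitimate primary endpoint for a regional therapy.** Agreed. It then needs a regional benchmark, and the plan gives none.

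**Conclusion.** The concern holds as a mismatch between endpoint and benchmark, not as an error in the power calculation. The 0.10 level and 80% power apply to PFS with all events counted; they do not carry over to the claim that IP-PFS exceeds what chemotherapy alone achieves.

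With no any-site advantage and extraperitoneal shares of 10% to 33%, the illustrative chance of apparent success runs from 0.12 to 0.44 when there are no deaths or deaths count. It runs from 0.35 to 0.69 when a 20% share of deaths goes uncounted. The comparator is 0.076. These figures rest on constant hazards, uncounted events that leave the later IP hazard unchanged, the review's own success rule, and shares the documents do not supply. The direction within the same patients rests only on counting fewer events. Applying it to the 5.0-month figure rests on the inference that this PFS counts any site and death.

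**What to change.** 1. In section 8, make the 5.0 versus 10 month comparison, with its alpha and power, on any-site PFS: surgery to first progression at any site or death. This matches the purpose stated in the precis and section 1.2.5.
2. Use the scheduled follow-up imaging, and state that it covers chest, abdomen and pelvis as at baseline (2.2.2). Section 3.11 asks only for imaging studies, so a reader should not assume that chest coverage is already secured.
3. Keep IP-PFS as the regional endpoint, defined once and identically in 1.1.1, 3.11 and 8: which sites count, including liver, and how death is handled. Report it separately. Do not judge it against 5.0 months unless an IP benchmark is justified and the power restated.
4. Record the site of first progression. Count extraperitoneal progression that leads to off-study status under 3.13.2 as an event for any-site PFS. For IP control treat it as a competing event, for example with cumulative incidence curves, and not as non-informative censoring.

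**Cost.** Text in three sections, a counting rule tied to 3.13.2, one data field and one extra curve; no additional patients. Chest coverage at follow-up has to be confirmed, and the headline median may be less favourable. The difference in population from the historical trial remains: evaluable patients here must have been successfully debulked and have received HIPEC. It should be stated as a limitation, because any-site PFS removes the endpoint mismatch only.
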